9.1.3 Serious Adverse Events (SAEs)

A serious adverse event (SAE) is one that meets one or more of the following criteria:

- Results in death.
- Is life-threatening (places the subject at immediate risk of death from the event as it occurred).
- Results in inpatient hospitalization or prolongation of existing hospitalization.
- Results in a persistent or significant disability or incapacity.
- Results in a congenital anomaly or birth defect.
- An important medical event that may not result in death, be life threatening, or require hospitalization may be considered an SAE when, based upon appropriate medical judgment, the event may jeopardize the subject and may require medical or surgical intervention to prevent one of the outcomes listed in this definition.

9.2 Time Period and Frequency for Event Assessment and Follow-Up

AEs, UPs, and SAEs will be recorded in the data collection system throughout the study. Events will be followed for outcome information until resolution or stabilization.

The Study PI will record all reportable events with start dates occurring any time after informed consent is obtained until seven (for non-serious AEs) or 30 days (for SAEs) after the last day of study participation. Parents/caregivers will be instructed to report

any doctor office or emergency room visits in the three days after the fluoride varnish application. At the 6- and 12-month follow-up study visits, the staff will inquire about the occurrence of AE/SAEs including FV-related AE/SAEs since the last visit. Events will be followed for outcome information until resolution or stabilization.

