2.3 Potential Risks and Benefits

2.3.1 *Potential Risks*

This study poses minimal risk to participants. Study participation is completely voluntary, and participants may discontinue participation at any time without prejudice. Regarding study questionnaires, parent participants may experience psychological discomfort in discussing personal health information or negative experiences at a dental or other relevant office (such as enrolling a child in Medicaid). As with any study, there is the potential for loss of confidentiality. Appropriate precautions will be taken to mitigate this risk. Parents/guardians will be reminded not to change the app profile study ID number to any personal identifying information; if they do it will be transmitted to Philips Sonicare. These include the use of unique study codes for participants and password-protected computers for data storage. Compliance with all Institutional Review Board (IRB) regulations concerning data collection, data storage, and data destruction will be strictly observed. Data will be accessible to research personnel only and will be stored and coded according to guidelines set forth by the UCSF IRB.

The child participant could have potential mechanical trauma to the teeth or gingiva from the powered toothbrush. Parents will be carefully instructed on proper brushing techniques to reduce possible oral discomfort.

Additionally, there is a rare chance of tooth brush head disintegration (bristles falling out), which is a potential choking hazard. The powered toothbrush should always be used with adult supervision, and children should be discouraged from chewing on the brush head.

Even though it is extremely unlikely that a child will get access to and eat the TP, using TP pumps will further reduce the chance of toxicity since the pumps require dexterity that children in the study age range likely lack, and the pumps limit the amount of TP dispensed at any one time. Parents will be advised to keep the TP on a counter and out of the reach of all children in the household.

There is a possibility that a participant may experience an allergic reaction to the TP, FV, and/or plaque disclosing solution; however, the likelihood from TP and FV is extremely rare, while the likelihood from disclosing solution is also rare according to the package insert. Parents/caregivers will be instructed to contact the study's Project Manager in the unlikely event that an allergic reaction to a study product is suspected.

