In the Delayed Monetary Reward Control group, participants will receive feedback on their toothbrushing performance during the first 12 months of the trial. After the Month 12 follow-up visit, the Control group participants will have the option to participate in a delayed 6-month extension by being randomized to one of two groups to earn the same expected monetary rewards the intervention group was eligible to earn through Month 6; both Control groups will have weekly drawings (as in the intervention group though 6 months), but one Control group will be randomized into drawing results shared weekly (as in the intervention group through 6 months), while the other randomized Control group will have the 13 weekly drawing results only shared quarterly, with equal reward amounts and the same probabilities for high and low thresholds.

Toothbrushing performance will be ascertained via Philips Sonicare for Kids (S4K) powered toothbrushes and brush heads, which will be synced with a custom BEECON study version of their existing S4K smartphone application. Data to be transmitted includes toothbrushing start time, toothbrushing duration, application start time, and whether toothbrushing was conducted with the application open or without the application (offline).

SMS text message notifications will be sent via Twilio and REDCap to remind participants to sync the powered toothbrush to the smartphone app. Further, all study participants will be sent weekly SMS text messages with feedback on toothbrushing progress, and, if in the intervention group, the incentives earned.

Additionally, participants will undergo study visits every 3 months. At screening and Month 6, 12, and 18 visits the participating child will receive an ASTDD BSS dental screening after parents/caregivers provide a brief child medical history, and a OHI-MIS plaque score will be determined. Participants in each group will be provided a new TP pump at the Month 6 and Month 12 visits and 1 new brush head at each study visit (every 3 months). Questionnaires will be configured in REDCap.

Four focus group discussions (FGDs) of trial participants will be conducted after the Month 6 visit, and two FGDs of intervention arm participants will be conducted after the Month 12 visit. Participants will be chosen based on study performance (e.g., above and below high and low thresholds of toothbrushing adherence).

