7.2 Intermediate Visits

7.2.1 Month 3 Follow-Up Study Visit (Visit 2, $T = \text{business day } 65 \pm 28$)

During this Month 3 follow-up visit, the following procedures will be completed by trained staff members.

- Administer CAPI questionnaire to parent/caregiver.
- Dispense new brush head.
- Dispense earned rewards to the parent/caregiver (*Intervention Arm*).
- Dispense syncing payments to the parent/caregiver (*both groups*).
- Schedule the family’s next visit (in approximately 3 months) and give the parent/caregiver \$30 compensation for attending the 3-month visit.

7.2.2 Month 6 Follow-Up Study Visit (Visit 3, $T = \text{business day } 130 \pm 28$)

During the Month 6 follow-up visit, the following procedures will be completed by trained staff members.

- Perform follow-up assessments of outcome measures and safety.
- Administer CAPI questionnaire to parent/caregiver.
- Record medical history and perform ASTDD BSS dental screening on child participant’s teeth (by blinded dental provider); record decay and assess treatment urgency. Children with urgent treatment needs will be referred with a warm handoff to staff at the corresponding dental clinic.

- Apply plaque disclosing agent to child's teeth (by blinded dental provider).
- Take extraoral photograph(s) of the facial surfaces of child's anterior teeth.
- Brush off plaque disclosing solution.
- Apply FV to the child's teeth (by dental provider).
- Have the parent/caregiver watch the Anticipatory Guidance presentation on a tablet.
- Record weight of TP pump.
- Dispense new toothbrush head and TP pump.
- Dispense earned rewards to the parent/caregiver (*Intervention Arm*).
- Dispense syncing payments to the parent/caregiver (*both groups*).
- Schedule the family's next visit (in approximately 3 months) and give the parent/caregiver \$30 compensation for attending the 6-month visit.
- After this visit, perform FGDs and stakeholder interviews

7.2.3 Month 9 Follow-Up Study Visit (Visit 4, T = business day 195 ± 28)

During the Month 9 follow-up visit, the following procedures will be completed by trained staff members.

- Administer CAPI questionnaire to parent/caregiver.
- Dispense new toothbrush head.
- Dispense earned rewards to the parent/caregiver (*Intervention Arm*.)
- Dispense syncing payments to the parent/caregiver (*both groups*).
- Schedule the family's next visit (in approximately 3 months) and give the parent/caregiver \$30 compensation for attending the 9-month visit.

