7.2.4 Month 12 Follow-Up Study Visit (Visit 5, T = business day 260 ± 28)

The Month 12 visit is the final study visit for participants randomized to the incentive group. During this visit, a trained staff member will complete the final questionnaire and post-test with the parent/caregiver.

- Administer CAPI questionnaire to parent/caregiver.
- Collect the TP pump. Record weight of TP pump.
- Record medical history and perform ASTDD BSS dental screening on child participant's teeth (by blinded dental provider); record decay and assess treatment urgency. Children with urgent treatment needs will be referred with a warm handoff to staff at the corresponding dental clinic.
- Apply plaque disclosing agent to child's teeth (by blinded dental provider).
- Take extraoral photograph(s) of the facial surfaces of child's anterior teeth.
- Brush off plaque disclosing solution.
- Apply FV to the child's teeth (by dental provider) (Continuing delayed control arm only).
- Give the parent/caregiver an electronic tablet to watch the Anticipatory Guidance presentation.
- Give the parent/caregiver the accumulated rewards (*Intervention Group*).
- Distribute 1 new toothbrush head and new TP pump.
- Dispense syncing payments to the parent/caregiver (*both groups*).
- Give the parent/caregiver \$30 compensation for attending this 12-month visit.
- After this visit, perform FGDs.
- *Optional for Control Group only:* Randomize Control Group participants who want to continue into 1 of 2 groups: weekly or quarterly drawing result communication. Explain the intervention procedures and Monetary Rewards program to the parent/caregiver and have her/him explain it back in her/his own words (teachback). Schedule the family's next visit (in approximately 3 months).

7.2.5 Month 15 Follow-Up Study Visit (*Optional for Control Group Only, Visit 6, T = business day 325 ± 28*)

During this Month 15 follow-up visit, the following procedures will be completed by trained staff members.

- Administer CAPI questionnaire to parent/caregiver.

- Dispense new toothbrush head.
- Dispense earned rewards to the parent/caregiver.
- Dispense syncing payments to the parent/caregiver.
- Schedule the family's next visit (in approximately 3 months) and give the parent/caregiver \$30 compensation for attending the 15-month visit.

7.2.6 *Month 18 Follow-up Study Visit (Optional for Control Group Only, Visit 7, T = business day 390 ± 28)*

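### Scheduled adverse-event enquiry is limited to Months 6 and 12 and reaches back only to the last visit, so read literally it misses the periods after varnish and early brush use; on any reading it stops at Month 12 for continuing controls

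*Combined protocol and SAP*

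**What the plan says.** Section 9.2 fixes when staff ask: "At the 6- and 12-month follow-up study visits, the staff will inquire about the occurrence of AE/SAEs". It fixes the recall period in the same sentence: "the staff will inquire about the occurrence of AE/SAEs including FV-related AE/SAEs since the last visit".

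Section 4 sets the visit frequency: "participants will undergo study visits every 3 months". Section 7.2 makes Months 3 and 9 numbered visits with their own procedure lists. The Month 3 list opens with "During this Month 3 follow-up visit, the following procedures will be completed by trained staff members", and neither list contains a safety step. The only such step in the section 7 lists is a general outcome-and-safety assessment at Month 6 (7.2.2).

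Varnish is listed at screening (7.1.1), at Month 6 (7.2.2), and at Month 12 with the restriction "by dental provider) (Continuing delayed control arm only" (7.2.4). The powered brush is handed out at screening (7.1.1), before the two-week run-in. Section 2.3.1 recognises a brush risk: "The child participant could have potential mechanical trauma to the teeth or gingiva from the powered toothbrush". It also mentions oral discomfort and shed bristles as a choking hazard.

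Outside the two enquiries, section 9.2 requires events to be recorded from consent onward and tells parents to report doctor or emergency-room visits within three days of varnish. Section 2.3.1 tells them to contact the Project Manager about a suspected allergic reaction. Section 9.1 calls for a log of events temporally associated with study varnish.

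**The concern.** The enquiry is meant to pick up varnish-related events, yet no varnish is given at Month 3 or Month 9, the visits from which its recall literally starts. Each listed application falls at the start of an interval that the enquiry does not reach. So do the first weeks with a new powered brush in children who may be as young as 6 months.

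In those intervals the plan relies on parents coming forward. The two instructions they receive concern medical visits soon after varnish and suspected allergy. Neither prompts for gum trauma, discomfort or bristle loss, which are the events section 2.3.1 links to the brush and the ones least likely to lead to a medical visit.

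What is at stake is the completeness of the safety record. Section 9.3.2 makes frequency one of the grounds for calling an event unexpected, and section 10 has the DSMB assess safety data. A frequency built partly on prompted and partly on volunteered reports is hard to interpret.

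**Working it through.** The plan states no coverage figure to reproduce, so this check maps the nominal visit days onto the two recall windows.

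**Inputs (sections 7.1 and 7.2, business days).** Screening -10; baseline 0; Month 3 = 65; Month 6 = 130; Month 9 = 195; Month 12 = 260; optional Month 15 = 325 and Month 18 = 390. Follow-up visits have a window of ±28 days. Varnish is listed at -10, 130 and, for continuing controls, 260.

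**Literal reading (last visit = preceding study visit).**
- Month 6 enquiry: 130 - 65 = 65 days.
- Month 12 enquiry: 260 - 195 = 65 days.
- Covered: 65 + 65 = 130. Screening to Month 12: 260 + 10 = 270. Coverage 130/270 = 48%; unasked 140/270 = 52%.
- For a control followed to Month 18: 390 + 10 = 400, and 130/400 = 32.5%.
- Brush use before the first window: 65 + 10 = 75 days. With the Month 3 window the range is 65 - 28 + 10 = 47 to 65 + 28 + 10 = 103.

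**Alternative reading (last visit = preceding dental and varnish visit).**
- Month 6 enquiry: 130 + 10 = 140 days.
- Month 12 enquiry: 260 - 130 = 130 days.
- Covered: 140 + 130 = 270 of 270 to Month 12. For a control followed to Month 18, 270/400 = 67.5%.

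**Are the listed varnish applications and the following three days inside a window?**

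| Application | Literal | Alternative |
|---|---|---|
| Screening, day -10 | No | Yes |
| Month 6, day 130 | No | Yes |
| Month 12, day 260 (continuing controls) | No | No |

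The bottom row does not depend on the reading: 390 - 260 = 130 business days have no specified enquiry.

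**Missed visits, literal reading.** If Month 9 is missed, the Month 12 enquiry reaches back to day 130 and takes in the Month 6 varnish. If Month 3 is missed, the Month 6 enquiry reaches back to day 0. That covers brush use after baseline but still not the screening varnish.

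**The case against.** The strongest reply is that the literal reading is not the intended one. Naming varnish-related events makes little sense unless the enquiry looks back to a visit at which varnish was given, and on that reading coverage to Month 12 is complete. This is a fair point and may well be the intent. But Months 3 and 9 are numbered study visits, the section does not define the term, and staff could apply it either way. The reply also leaves Months 12 to 18 open.

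Second, a reader might infer that events after varnish are not captured at all. The documents do not support that. Recording runs throughout the study, the three-day instruction is aimed at the period right after varnish, section 9.1 provides a varnish event log, and the Month 6 safety assessment carries no recall limit. Medical history and a dental screening are also listed at Months 6, 12 and 18, although the protocol does not describe them as AE enquiry. What is missing is a scheduled prompt.

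Third, silence in a visit list is weak evidence. The Month 12 list has no AE line either, yet section 9.2 requires the enquiry there. The questionnaires and Manual of Procedures are separate documents (Supplemental Materials), so an AE item at other visits cannot be ruled out. The protocol does not require one, and that is all that is claimed here.

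Fourth, a reader might infer that every child has two unasked varnish applications. That is too firm. Section 2.3.2 allows varnish to be omitted if the parent reports one within the past month, and section 8.8 moved visits to remote contact for part of the study. The extension is optional, and section 6.1 places it outside the formal trial. It nevertheless has listed visits, and varnish is listed for those entering it.

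**Conclusion.** The point holds as a defect of wording and scope. Read literally, scheduled enquiry covers 48% of the business days from screening to Month 12. It leaves the periods after the screening and Month 6 varnish, and about 75 business days of first brush use (47 to 103 with the visit window), to passive reporting. If the recall was meant to start at the previous dental and varnish visit, the gap to Month 12 closes, but the protocol needs to say so. On both readings, controls who continue have no specified enquiry for the 130 business days after Month 12.

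These figures assume nominal visit days and full attendance. The likely consequence is under-ascertainment of non-serious events. A reader might go further and conclude that reported AE counts are certain to be too low; no data in the documents show that, and the size of any shortfall cannot be derived from them. Nor is there reason to infer bias in the main comparison: the toothbrushing outcome does not depend on AE enquiry, both arms have the same brush and the same enquiry schedule to Month 12, and section 12.4 plans no tolerability analysis of the brush or varnish. The change is worth making on safety-reporting grounds.

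**What to change.** - In section 9.2, replace the recall phrase with *since the last AE enquiry (since consent at the first enquiry)*. This alone removes the ambiguity and closes the gap to Month 12.
- Add an AE enquiry at Months 15 and 18 for continuing controls.
- Preferably, put the same AE item in the questionnaire that section 8.3 already has staff give at every study visit, with a matching line in each section 7 visit list. Shorter recall should help with minor events such as sore gums, and the item can name the brush-related risks in section 2.3.1.

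The cost is a protocol wording change and one item in an existing interview, with no new visit or staff. The downside is a slightly longer interview and more minor events to log and grade. If some participants have already been followed under the current wording, the safety report should state which recall period staff actually used.

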9.3 Characteristics of an Adverse Event

9.3.1 Relationship to Study Intervention

To assess relationship of an event to study intervention, the following guidelines are used:

1. Related (Possible, Probable, Definite)
 - a. The event is known to occur with the study intervention.
 - b. There is a temporal relationship between the intervention and event onset.
 - c. The event abates when the intervention is discontinued.
 - d. The event reappears upon a re-challenge with the intervention.
2. Not Related (Unlikely, Not Related)
 - a. There is no temporal relationship between the intervention and event onset.
 - b. An alternate etiology has been established.

9.3.2 Expectedness of AEs

The study PI will be responsible for determining whether an AE is expected or unexpected. An AE will be considered unexpected if the nature, severity, or frequency of the event is not consistent with the risk information previously described for the intervention.

9.3.3 Severity of Event

Severity of Event: All reportable AEs will be assessed by a clinician study PI or co-investigator using the following guidelines to quantify intensity:

1. Mild: events require minimal or no treatment and do not interfere with the participant's daily activities.

2. **Moderate**: events result in a low level of inconvenience or concern with the therapeutic measures. Moderate events may cause some interference with functioning.
3. **Severe**: events interrupt a participant's usual daily activity and may require systemic drug therapy or other treatment. Severe events are usually incapacitating

9.4 Reporting Procedures

9.4.1 *Unanticipated Problem (UP) Reporting to IRB and NIDCR*

Incidents or events that meet the OHRP criteria for UPs require the creation and completion of an UP report form. OHRP recommends that PIs include the following information when reporting an AE, or any other incident, experience, or outcome as an UP to the IRB:

- Appropriate identifying information for the research protocol, such as the title, investigator's name, and the IRB project number;
- A detailed description of the AE, incident, experience, or outcome;
- An explanation of the basis for determining that the AE, incident, experience, or outcome represents an UP;
- A description of any changes to the protocol or other corrective actions that have been taken or are proposed in response to the UP.

To satisfy the requirement for prompt reporting, UPs will be reported using the following timeline:

- UPs that are (a) SAEs or (b) definitely, probably, or possibly related to study procedures will be reported to the UCSF IRB (CHR) and to NIDCR within 5 working days of a PI becoming aware of the event, unless life-threatening or resulting in death in which case they will be reported within 24 hours (according to SAE reporting procedures outlined in 9.4.2).
- All UPs should be reported to appropriate institutional officials (as required by an institution's written reporting procedures), the supporting agency head (or designee), and OHRP within one (1) month of the IRB's receipt of the report of the problem from a PI.

All UPs will be reported to NIDCR's centralized reporting system via Rho Product Safety:

- Product Safety Fax Line (US): [name]
- Product Safety Fax Line (International): [name]
- Product Safety Email: [contact]
- CC Safety Email: [contact]
- CC Safety Fax Line: [name]

General questions about UP reporting can be directed to the Rho Product Safety Help Line (available 8:00AM – 5:00PM Eastern Time):

- US: [name]
- International: [name]

9.4.2 Serious Adverse Event Reporting to IRB and NIDCR

In the unlikely event that an AE or SAE incident occurs during this study, any AE meeting the specified SAE criteria will be submitted within 5 work days of a PI's awareness in the UCSF electronic IRB system to the UCSF CHR and on an SAE form to NIDCR's centralized safety system via Rho Product Safety. This report may be sent by fax or email. Once submitted, Rho Product Safety will send a confirmation email to the PIs within one (1) business day. The investigator should contact Rho Product Safety if this confirmation is not received. This process applies to both initial and follow-up SAE reports.

SAE Reporting Contact Information:

- Product Safety Fax Line (US): [name]
- Product Safety Fax Line (International): [contact]
- Product Safety Email: [contact]
- CC Safety Email: [contact]
- CC Safety Fax Line: [name]

General questions about SAE reporting can be directed to the Rho Product Safety Help Line (available 8:00AM – 5:00PM Eastern Time):

- US: [name]

- International: [contact]

The study clinician will complete a SAE form and submit via fax or email within the following timelines:

- All deaths and immediately life-threatening events, whether related or unrelated, will be recorded on the SAE form and submitted to Product Safety within 24 hours of site awareness.
- SAEs other than death and immediately life-threatening events, regardless of relationship, will be reported by fax within 5 work days of site awareness.

All SAEs will be followed until resolution or stabilization.

9.4.3 *Reporting of SAEs and AEs to FDA*

Any AE meeting the specified SAE criteria and being rated as related (possible, probable, definite) to FV administration will be submitted to the FDA using the MedWatch voluntary reporting system (<https://www.accessdata.fda.gov/scripts/medwatch/index.cfm?action=reporting.home>).

9.4.4 *Events of Special Interest*

Suspected child abuse reporting is mandatory because the study participants include minors; any incidents will be reported to an EHS or day care center supervisor. California law stipulates that a provider seeing a child as a patient is not required to report domestic violence or abuse of the parent/caregiver. But the parent/caregiver may choose to make his/her own report by contacting police. We do not anticipate any other events of special interest during the short duration of this study.

